5.4 Subject Death

5.4.1 Procedure for recording and reporting Subject Death

All subject deaths are to be documented and reported to the sponsor according to the reporting requirements for all SAEs and SADEs (Refer to Adverse Events Reporting section).

Should death occur, the investigator is requested to record death information in the hospital records and immediately document the information on the Death form. By completing the form the sponsor will be notified.

Refer to table 1 'Data Collection' and Appendix D 'Data Collection Method'

In case of EDC failure, notify Sponsor via Fax (please refer to the Investigator Site Binder, section 0.1 "Sponsor Contact Details" for further details about Fax numbers).

Subject Death can be an outcome of a serious adverse event (SAE) or serious adverse device effect (SADE).

- Death is therefore related to an SAE/SADE: all efforts to obtain the SAE/SADE details should be made and the Adverse Event form must be completed.
- The subject's death is an Early Conclusion of the subject's participation in the investigation. Therefore, the investigator is requested to complete the Termination form.
- The investigator must notify the EC / IRB, if appropriate, in accordance with national and local laws and regulations.

5.5 Criteria and procedures for subject withdrawal or discontinuation

Each subject should remain in the investigation until completion of the required follow up period; however, a subject's participation in the investigation may be discontinued. Should this occur, the reason for discontinuation must be documented in the source documents.

Subjects must be informed about their right to withdraw from the investigation at any time and for any reason without sanction, penalty or loss of benefits to which the subject is otherwise

entitled and withdrawal from the investigation will not jeopardize their future medical care or relationship with the investigator. Subjects will be asked to specify the reason for the termination, but have the right not to answer.

The investigator may decide to withdraw a subject from the investigation at any time.

The subject's future care will not be influenced by a decision, voluntary or otherwise, to withdraw from the investigation. All reasonable efforts should be made to retain the subject in the clinical investigation until completion of the investigation.

Reasons for subject's withdrawal include, but are not limited to:

- Subject refuses to continue participating in the investigation (refuse all subsequent testing/follow up)
- Subject does not meet the inclusion/exclusion criteria
- Subject's baseline Echo or 6 Month Echo is not analyzable or evaluable according to the Echo Core Lab.
- Subject had Permanent AF at the time of enrollment and no ablation has been performed within 2 weeks after the CRT implant
- Subject does not have a successful implant
- Subject does not meet criteria for turning MPP feature on
- Subject is deceased (cause must be documented)
- Subject's non-compliance
- Subject's participation is terminated by the PI or investigator, although the subject consented, since participation is no longer medically justified
- Subject is 'lost to follow up': Subject does not adhere to the scheduled follow up visits but has not explicitly requested to be withdrawn from the clinical investigation. (This does not apply to missed visits). Site personnel should at all times make all reasonable efforts to locate and communicate with the subject in order to achieve patient compliance to the scheduled follow up visits:
 1. A subject will be considered 'Lost to Follow Up' after a minimum of 2 phone calls of a physician or delegate at the investigational site to the subject or contact. These 2 phone calls need to be documented in the patient's hospital records.
 2. If these attempts are unsuccessful, a certified letter should be sent to the subject's last known address or general practitioner (GP) and a copy of this letter should be maintained in the patient's hospital records.

If the subject misses two consecutive scheduled follow up visits and the above mentioned attempts to contact the subject/GP were unsuccessful, the subject will be considered 'Lost to Follow Up' and subject's Withdrawal form should be completed. The investigator ensures that all attempts are documented in the patient's hospital records.

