3.4 Investigational Type

This study is designed as a Prospective, Randomized, Multi-center Trial.

Data will be collected at Enrollment, Baseline, Implant Procedure, Patient Classification, 6 Months and 12 Months Follow-Up.

During the Enrollment visit, the Informed Consent Procedure will be performed and the Inclusion/Exclusion criteria verified.

During the Baseline visit the demographic data, medical history, clinical data and procedure details will be collected.

After the Implant Procedure, the Patient Classification will be performed in order to identify the Qualified Subjects that will constitute the Study Population.

During the 6 Months visit, the subject's response to CRT will be evaluated at the center level according to LVESV reduction. Before randomization in the second phase of the study, all subjects will undergo testing to determine if the mandated MPP settings can be programmed (see below for MPP programming requirements in Phase II). For those subjects in whom the mandated MPP settings cannot be programmed before randomization at 6 months, their participation in the study will end (an early termination form must be completed).

- Subjects with a LVESV reduction of at least 15% will be classified as **RESPONDERS**. For those subjects, their participation in the study will end (if confirmed by the Core Lab), and they will then return to the center's routine follow up schedule/practice.
 - If the subject is evaluated as a Responder by the center and later as a Non Responder by the Core Lab, the center must randomize the subject and should call the subject back for an unscheduled visit (see 4.2.7) in case the randomization assignment is different from programmed.
- Subjects with an LVESV reduction of less than 15% will be classified as **NON RESPONDERS**. These subjects should be randomized and the device programmed to either MPP OFF or MPP ON per the randomization assignment (Please refer to section 3.8 "Randomization Procedure" for further details).
 - If the subject is evaluated as a Non Responder by the center and later as a Responder by the Core Lab, the subject continues to 12 Months visit but the data are excluded from the primary endpoint analysis.
- For those subjects randomized to MPP ON in the second phase of the study, the MPP feature should be programmed as follows:

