3.7 Subject Enrollment Classification

Once the eligible subject has signed the Informed Consent and completed the Baseline visit, he/she will advance to the Implant Procedure and Patient Classification visit in which the CRT device implant and MPP activation tests will be performed. Depending on the result of the Patient Classification, the subjects will be classified as:

- **Eligibility Failure:**
Patients who provided the Informed Consent but failed to meet the Inclusion/Exclusion Criteria. These subjects' participation to the study will be terminated immediately.
- **Implant Failure:**
Patients who provided the Informed Consent, meet the Inclusion/Exclusion criteria, but do not receive the CRT MPP compatible device because of implant failure or physician's decision. These subjects' participation to the study will be terminated immediately.
- **MPP Activation Failure:**
Patients who provided the Informed Consent, meet the Inclusion/Exclusion Criteria, have been implanted with a CRT MPP compatible device but not enough MPP vector combinations are possible to allow the MPP activation. These subjects' participation to the study will be terminated immediately.
- **Qualified Subject:**
Patients who provided the Informed Consent, meet the Inclusion but not the Exclusion criteria, have been implanted with a CRT MPP compatible device, have MPP vector combinations to allow the MPP activation. These subjects will proceed in the study and constitute the Study Population.

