4.1 Investigation Flow Chart

4.2 Protocol Activities

The following table lists all electronic Case Report Forms (eCRFs) that are to be completed during the respective visits. Mandatory eCRFs are identified with an “X”. eCRFs that are optional or have to be completed only in case of a certain event (i.e. Adverse Event) are marked with an “(X)”

CRFs \ Visit	Visit						
	Enroll	Baseline	Implant Proc.	Patient Classification	6 Months FU	12 Months FU	Unsch FU
Enrollment Form	X						
Implant Form			X				
Patient Classification Form				X			
Baseline Form		X					
Echocardiography Form		X [§]			X	X	(X)
EQ-5D Form		X			X	X	(X)
MLWHF Form		X			X	X	(X)
Follow Up Form					X	X	(X)
System Revision Form			(X)	(X)	(X)	(X)	(X)
Deviation Form	(X)	(X)	(X)	(X)	(X)	(X)	(X)
Adverse Event Form	(X)	(X)	(X)	(X)	(X)	(X)	(X)
Termination Form	(X)	(X)	(X)	(X)	(X)	(X)	(X)
Death Form	(X)	(X)	(X)	(X)	(X)	(X)	(X)

(X): If applicable

X[§]: Baseline Echocardiography can be performed at any time from 3 months prior CRT implant (by an echo qualified study center).

Table 1: Data Collection: eCRF requested per visit

All the mandatory activities/procedures are listed in the following table and detailed in the next pages:

	Enroll	Baseline	Implant Proc.	Patient Classification	6 Month FU	12 Month FU
Informed Consent procedure	X					
Inclusion/Exclusion Criteria check	X					
Implant Procedure Details			X			
Fluoroscopy Images Collection (LAO and RAO – EDC upload)			X			
Implant Procedure Success Confirmation				X		
MPP Vector Test				X	X [§]	
Patient Data and Medical History		X				
Current Cardiac Medications		X				
Changes in Cardiac Medications					X	X
Patient Global Assessment					X	X
NYHA Class Evaluation		X			X	X
Randomization procedure (only for Non Responders to CRT)					X	
12-Lead ECG (EDC upload)		X			X	X
BNP/pro-BNP/ NT-pro-BNP Test *		(X*)			(X*)	(X*)
6 Minutes Hall Walking Test		X			X	X
EQ-5D Questionnaire		X			X	X
MLWHF Questionnaire		X			X	X
Echocardiography		X [§]			X	X
Preliminary LVESV Evaluation		X			X	
Conduction Delays Test			X	X	X	X
Device Test and Programming (EDC upload)			X	X	X	X
MPP Programming			X	X	X	

(X*): If performed as Standard of care at the site

X[§]: Testing of mandated MPP settings in Phase II before randomization (see section 4.2.5 for further details)

X[§]: can be performed at any time from 3 months prior CRT implant (by an echo qualified study center)

Table 2: List of all required activities/procedures

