Informed Consent Procedure and Inclusion/Exclusion Criteria check:

Patient's eligibility criteria and Informed consent Procedure is performed before any study related activity. Please refer to section 4.2.1 "Enrollment visit" for further details.

Implant Procedure Details:

Implant Procedure details (standard CRT implant) will be collected at Implant visit. Indicate model n°, serial n° and date of implant of entire implanted system (CRT device, RA lead, RV lead and LV lead), even in case of implant failure. Final positions of all the implanted leads must be specified: right atrium, right ventricle and left ventricle lead positions.

Fluoroscopy Images Collection (EDC upload):

As the lead placement is important to understanding the subject's response to CRT, two anonymized Fluoroscopy images are requested to be collected:

- LAO (Left Anterior Oblique, $45^{\circ}\pm 10^{\circ}$)
- RAO (Right Anterior Oblique, $45^{\circ}\pm 10^{\circ}$).

The position of all leads must be clearly visible to allow matching with the venous anatomy. These anonymized images should be uploaded to the EDC system using the feature "Attachments to CRFs", for further details on this topic please refer to Appendix E "Guidelines" part 1.1.

Implant Procedure Success Confirmation:

In the Patient Classification visit, the confirmation of a successful implant procedure will be asked in order to classify the subject as Qualified Subject or not.

MPP Vector Test:

In order to allow future activation of MPP, specific LV pacing capture thresholds and Phrenic Nerve Stimulation (PNS) tests must be performed for the 4 cathodes during the Patient Classification visit.

The test is considered positive in case is possible to identify at least 2 vectors from different Groups (with different Cathodes) free from Phrenic Nerve Stimulation (PNS) and with a Pacing Threshold that do not exceed 4.5V at 0.5ms pulse duration in CRT-D devices and at 0.4ms pulse duration in CRT-P devices.

Please refer to Appendix E "Guidelines" part 6 for the detailed testing procedure.

Subject Data and Medical History:

Subject's Year of Birth and Gender will be collected at the Baseline visit together with cardiomyopathy etiology and co-morbidities.

Current Cardiac Medications/Changes in Cardiac Medications:

The current cardiac medications will be collected at Baseline, while during the Follow-up Visits only the changes will be documented.

Patient Global Assessment:

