 - b. Read the first question to the patient - "Did your heart failure prevent you from living as you wanted during the last month by causing swelling, for example, in your ankles, legs"? Tell the patient, "If you did not have any ankle or leg swelling during the last month you should circle nought after this question to indicate that swelling was not a problem during the last month". Explain to the patient that if he or she did have swelling that was caused by a sprained ankle, or some other cause that was definitely not related to heart failure, he or she should also circle nought. Tell the patient, "If you are not sure why you had the swelling or think it was related to your heart condition, then rate how much the swelling prevented you from doing things you wanted to do and from feeling the way you would like to feel". In other words, how bothersome was the swelling? Show the patient how to use the 1 to 5 scale to indicate how much the swelling affected his or her life during the last month - from very little to very much.
4. Let the patient read and respond to the other questions. The entire questionnaire may be read directly to the patient, being careful not to influence responses by verbal or physical cues.
5. Check to make sure the patient has responded to each question and that there is only one answer clearly marked for each question. If a patient elects not to answer a specific question(s) indicate so on the questionnaire.
6. Score the questionnaire by adding the responses to all 21 questions. In addition, physical (items 2, 3, 4, 5, 6, 7, 12 and 13) and emotional (items 17, 18, 19, 20, and 21) dimensions of the questionnaire have been identified by factor analysis, and may be examined to further characterize the effect of heart failure on a patient's life.

These questions concern how your heart failure (heart condition) has prevented you from living as you wanted during the last month. The items listed below describe different ways some people are affected. If you are sure an item does not apply to you or is not related to your heart failure, then circle 0 (No) and go on to the next item. If an item does apply to you, then circle the number relating to how much it prevented you from living as you wanted.

Part 6: MultiPoint Pacing Vectors Test

This appendix describes the test procedure (Vector Test) that needs to be performed in order to establish if the MPP feature can be turned ON. The feature will be tested at the Classification visit.

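### Protocol 5.5 does not limit inability to activate MPP as a withdrawal reason to before randomization; in Phase I it would then be met systematically only in the MPP ON arm

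*Combined protocol and SAP*

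**What the plan says.** - **First MPP check, both phases.** Protocol 4.2 states that "specific LV pacing capture thresholds and Phrenic Nerve Stimulation (PNS) tests must be performed for the 4 cathodes during the Patient Classification visit". Section 4.2.4 puts that visit within 7 days of implant. Appendix E Part 6, which describes the vector test, agrees: "The feature will be tested at the Classification visit".
- **Failing that check.** Section 3.7 defines MPP Activation Failure as patients who "have been implanted with a CRT MPP compatible device but not enough MPP vector combinations are possible to allow the MPP activation". Their participation ends at once, about six months before randomization.
- **Check at 6 months.** Section 3.4 says: "Before randomization in the second phase of the study, all subjects will undergo testing to determine if the mandated MPP settings can be programmed". The Table 2 footnote has the same limit: "Testing of mandated MPP settings in Phase II before randomization". No equivalent is described for Phase I.
- **After randomization.** Section 4.2.5 has subjects assigned MPP ON programmed before they leave hospital and refers the site to Appendix E Parts 6 and 7 for activation. It gives no such instruction for MPP OFF. SAP 3.0 leaves Phase I programming to the physician.
- **Withdrawal.** Section 5.5 lists "Subject does not meet criteria for turning MPP feature on" with no time, phase or arm attached, and adds: "The investigator may decide to withdraw a subject from the investigation at any time". It also asks sites to make reasonable efforts to retain subjects.
- **Analysis.** Protocol 7.4 removes from the primary analysis anyone who does not complete follow-up for a reason other than cardiac death. Protocol 7.6 rules out imputation.

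**The concern.** Capture thresholds and phrenic nerve stimulation can change, and leads can move, between the first week and month 6. In Phase II such a change is looked for before allocation, in all subjects, so any loss is independent of arm. In Phase I the first occasion on which the plan requires MPP to work is after allocation, and only in the ON arm. The 5.5 reason is open at that moment, and 7.4 turns a withdrawal into an exclusion from the primary analysis.

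That is a route to exclusion after randomization in one arm. If the subjects who take it are less likely to remodel, the ON group loses some of its poor responders while the OFF group keeps its own, and the Phase I comparison leans toward MPP.

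**Working it through.** **Step 1. Who meets the reason, and when**

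| Moment | Phase I | Phase II |
|---|---|---|
| Patient Classification | Vector test, all implanted subjects | Same |
| 6 months, before randomization | No MPP check described | Test of mandated settings, all subjects |
| 6 months, after randomization | Activation in ON only | Activation in ON only, after a passed test |

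The 5.5 list is not confined to the period around implant: it also includes a 6-month echo that cannot be evaluated. The Phase II rule in 3.4 and 4.2.5 is expressly placed before randomization; the 5.5 reason is not.

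**Step 2. Formula**

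The plan states no figure for this point, so there is none to reproduce. Response rates and sample-size inputs are redacted. Let f be the share of Phase I randomized subjects in whom MPP cannot be activated at 6 months, p the response rate in the others, and pf the rate in those subjects. Assume no true MPP effect, that all ON failures are withdrawn, and that all OFF failures stay.

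- ON rate as analysed: p
- OFF rate as analysed: (1 − f)p + f·pf
- Spurious difference: p − [(1 − f)p + f·pf] = f(p − pf)

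**Step 3. Numbers (all assumed), with p = 30%**

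| f | pf = 15% | pf = 5% | pf = 30% |
|---|---|---|---|
| 2% | 0.02 × 0.15 = 0.3 points | 0.02 × 0.25 = 0.5 points | 0 |
| 5% | 0.05 × 0.15 = 0.75 points | 0.05 × 0.25 = 1.25 points | 0 |
| 10% | 0.10 × 0.15 = 1.5 points | 0.10 × 0.25 = 2.5 points | 0 |

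Over a wider grid (p 20 to 40%, f 1 to 10%, pf from 0 to p) the difference runs from 0 to 4.0 points. If only some ON failures are withdrawn, it is smaller.

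**Step 4. Effect on the test**

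SAP 5.1.1 uses a 97.5% lower Wald bound, that is, one-sided alpha 1 − 0.975 = 0.025. Assume 250 per arm, p = 30%, f = 5%, pf = 15%:

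- OFF rate = 0.95 × 0.30 + 0.05 × 0.15 = 0.2925; difference = 0.0075
- ON subjects analysed = 250 × 0.95 = 237.5
- SE = √(0.30 × 0.70/237.5 + 0.2925 × 0.7075/250) = 0.0414
- Actual alpha = 1 − Φ(1.960 − 0.0075/0.0414) = 0.038

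With the same p, pf and arm size, f = 2% gives 0.030 and f = 10% gives 0.055. With pf = 0, f = 5% gives 0.055 and f = 10% gives 0.108. With pf = p, alpha stays at 0.025.

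**Step 5. After the fix**

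If failures are kept in both arms, the spurious difference is 0 and alpha is 0.025.

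**The case against.** The best defence is that the reason belongs to Patient Classification. In 5.5 it directly follows the unsuccessful-implant reason, the same order as in 3.7, and Appendix E Part 6 ties the activation criteria to that visit. Every randomized Phase I subject has already met them. This stands as the main use of the reason, and it narrows the gap to failures arising between that test and 6 months. It does not close the gap, because 5.5 sets no time limit and 4.2.5 sends ON subjects back to Part 6.

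The Phase II test also has a purpose of its own: it checks a specific mandated configuration, whereas Phase I needs only two workable vectors with different cathodes. Its absence in Phase I is therefore no oversight in itself, and Phase I failures may be few.

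Three stronger readings are tempting and are not supported:

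- *That assignment to ON triggers withdrawal.* Section 5.5 permits withdrawal and urges retention. No text directs that a randomized subject who cannot be activated must leave.
- *That an OFF subject is never tested.* Routine sensing, pacing and impedance measurements on all leads are made at 6 months in both arms and may reveal some failures. They are not described as a four-cathode threshold and phrenic nerve test.
- *That pooled results are biased too.* SAP 5.1.5 analyses Phase I on Cohort #1; the poolability analysis in 5.1.6 concerns Cohorts #2 and #3. The definitions are redacted, so this cannot be established.

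The SAP sensitivity analyses are redacted as well and may already deal with the issue. SAP 6.4 summarizes withdrawals, though the visible text does not say by arm.

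**Conclusion.** The concern holds in a limited form. The visible protocol text allows a Phase I subject randomized to MPP ON to be withdrawn because MPP cannot be activated, and then excluded from the primary analysis, with no matching step in the OFF arm. No passage says that such a subject stays and is analysed as randomized, so sites may differ.

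The bias in favour of MPP ON is 0.3 to 2.5 percentage points under the main assumptions (f 2 to 10%, p 30%, pf 5 to 15%). It needs two things that the documents do not show: that such failures occur and are withdrawn, and that these subjects respond less often. Without either, there is no bias. This is a cheap improvement that closes an avoidable route to exclusion, not evidence that the Phase I result is wrong.

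**What to change.** 1. In protocol 5.5, limit this withdrawal reason to the period before randomization: Patient Classification, or the Phase II test at 6 months.
2. In protocol 7.4 and the SAP analysis population, state that a subject randomized to MPP ON in whom MPP cannot be activated remains in follow-up to the 12-month echo and is analysed in the ON group.
3. Report by arm the number of Phase I subjects in whom MPP could not be activated, or who were withdrawn for this reason, and include any 12-month echo available for them.

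The cost is a sentence in 5.5, a sentence on the analysis population and one table. No new test or visit is needed; an added Phase I vector test would be a new procedure and is not proposed. Items 2 and 3 remain useful if Phase I randomization is already complete, as far as 12-month echoes exist. The downside is that the Phase I effect may become slightly smaller.
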